3.2 END OF STUDY AND LENGTH OF STUDY

The end of this study is defined as the date when the last patient, last visit (LPLV), occurs. The treatment period ends 3 years after the date the first patient enrolls in the study. The end of the study is expected to occur in second quarter of 2024.

In addition, the Sponsor may decide to terminate the study at any time.

The total length of the study, from enrollment of the first patient to the end of the study, is expected to be approximately 3 years and 3 months.

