4.5.6.2 Protocol-Defined Relapse

Protocol-defined relapse is the occurrence of new or worsening neurological symptoms attributable to NMOSD. Symptoms must persist for >24 hours and should not be attributable to confounding clinical factors (e.g., fever, infection, injury, change in mood, or adverse reactions to medications). New or worsening neurological symptoms that occur less than 31 days following the onset of a protocol-defined relapse will be considered part of the same relapse (i.e., if two relapses have onset days that are within 30 days of each other, they will be counted only as one relapse), and the onset date used in the analysis will be the onset date of the first relapse. The new or worsening neurologic symptoms must meet either of following:

1. An increase of at least 1.0 point on the EDSS score, or a 2.0 point increase on the EDSS if the EDSS score at baseline in the parent study was zero
2. An increase of at least 2.0 points on one of the appropriate FSS
3. An increase of at least 1.0 point on two or more of the appropriate FSS if the score at baseline in the parent study was one or more
4. An increase of at least 1.0 point in single eye FSS when the score at baseline in the parental study in that eye was one or more

The base of comparison for the increase is the score at the most recent scheduled EDSS/FSS assessment visit prior to the relapse. The appropriate FSS change must affect at least one of the following functional systems: pyramidal, cerebellar, brainstem, sensory, bowel/bladder, or visual (single eye). Sexual dysfunction and cerebral function will not suffice to establish a protocol-defined relapse.

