The ARR will be analyzed from randomization in ITT and from first dose of satralizumab in ALLSA. In both analyses the ARR is calculated as the total number of relapses experienced divided by the person-years of the whole study period. The unadjusted 95% CI will be presented based on the Poisson distribution.

For comparing the difference between the two treatment arms, negative binomial regression model will be used with ARR as response variable and treatment group, study ID of the parental study, and geographical region as covariates. In the ALLSA analyses, treatment group will not be included because all patients will receive satralizumab in this analysis.

In addition, the ARR by year of exposure will be estimated with use of a GEE Poisson regression model with repeated measurements and an unstructured covariance matrix, adjusted by Study Identifier of the parental study, and exposure year. Log-transformed patient years are included as an offset variable. In these analyses the overall ARR for the whole period is additionally estimated by a Poisson regression model. When comparing the difference between the randomized treatment arms of the parental studies, treatment is included as an additional covariate and the adjusted ARR and corresponding 95% CIs are presented for each arm and year.

All ARR analyses will be conducted for iPDRs, clinical relapses and treated clinical relapses.

Change in Expanded Disability Status Scale Score

The EDSS score will be assessed on scheduled visits during the study. The mean change in EDSS scores from randomization/first dose of satralizumab to every 24 weeks after the randomization/first dose of satralizumab visit will be analyzed.

Time to EDSS worsening based on the definition for PDR is estimated with a Cox regression with treatment group, and Study Identifier of the parental study as covariates. The HR and 95% CI for the treatment groups are estimated in this model, the p value is calculated on the basis of the stratified log rank test. In addition, Kaplan-Meier estimate of event-free rates will be provided for every 24 weeks and Kaplan-Meier curved will be estimated.

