These analyses are done for the double-blind period and the combined double-blind and OLE periods. When all randomized patients of both periods are analyzed together, patients are analyzed as randomized, even if patients randomized to placebo receive satralizumab in the OLE period. In addition, all patients are analyzed from first dose of satralizumab. In this case, only Kaplan-Meier estimate of event-free rates will be provided for every 24 weeks and Kaplan-Meier curved will be estimated since no comparison can be made.

In the same way, time to severe EDSS worsening is analyzed. Severe EDSS worsening is defined as a change of at least 2 points on the EDSS scale from randomization/first dose of satralizumab.

Change in Visual Acuity (Snellen Chart)

Visual acuity will be measured by a Snellen 20-foot wall chart. The test will be performed monocularly and patients may use their habitual distance glasses or contact lenses.

The same visual acuity testing method is to be employed for all study visits for each patient.

The mean change in logMAR Visual Acuity scores from randomization/first dose of satralizumab to every 24 weeks after the randomization/first dose of satralizumab visit will be analyzed.

Use of Acute Relapse/Rescue Therapy

The use of rescue therapy is based on treated clinical relapses. If a patient has at least one treated clinical relapse, then this patient is counted as a patient with rescue therapy use. The use of rescue therapy will be analyzed with a logistic regression model with treatment group, Study Identifier of the parental study and geographical region as covariates. The odds ratio, corresponding 95% CI, and p value for the treatment group

will be reported. This analysis will be conducted for the entire study period of each patient and also for the period after the first dose of satralizumab. In the analysis from first dose of satralizumab, treatment group will not be included as a covariate.

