		BL ^a	Every 4 weeks ^c	Every 12 weeks	Every 24 weeks	Delayed dosing ^d	Relapse assessment	Unscheduled assessments ^e	End of treatment ^f	
		Day 1	(±7)	(±7)	(±7)	-	-	-	-	(±7)
Informed consent	x									
Inclusion/exclusion criteria	x	x								
Demographic data		x								
Satralizumab injection (SC)		x	x ^h	x ^h	x ^h	x ^h				
Body weight and height ⁱ		x			x				x	x
Physical examination		x		x	x	x	x	x	x	x
Vital signs ^j		x		x	x	x	x	x	x	x
ECG ^k		x			x			x	x	x
Pregnancy test ^l		x		x	x			x	x	x
Laboratory tests ^m		x		x	x			x	x	x
Hepatitis B viral DNA ⁿ		x			x			x	x	x
C-SSRS		x			x			x	x	x
EQ-5D		x			x			x	x	x
EDSS/FSS		x			x		x	x	x	x
Adverse events	Monitor and record throughout the study									

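### Time to EDSS worsening counts a single unconfirmed rise, so event-free rates mix lasting disability with recovered relapses and, at the 1-point threshold, rater noise

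*Combined protocol and SAP*

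**What the plan says.** The disability endpoint is in Section 6.5, under the change in EDSS: "Time to EDSS worsening based on the definition for PDR is estimated with a Cox regression". The relapse definition it points to (Section 4.5.6.2) has four alternative score criteria, of which the EDSS one is "An increase of at least 1.0 point on the EDSS score, or a 2.0 point increase on the EDSS", the larger step applying when the parent-study baseline was zero. The only duration rule there is "Symptoms must persist for >24 hours", which concerns symptoms, not the score. On the reference score that section says: "The base of comparison for the increase is the score at the most recent scheduled EDSS/FSS assessment visit prior to the relapse".

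A second endpoint is analysed in the same way: "Severe EDSS worsening is defined as a change of at least 2 points on the EDSS scale from randomization/first dose of satralizumab".

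On timing, Appendix 1 schedules EDSS/FSS at baseline and "Every 24 weeks", and also at relapse, unscheduled, end-of-treatment and follow-up visits. Section 3.2 states that "The treatment period ends 3 years after the date the first patient enrolls in the study". Section 6.5 pools this study with both parent studies and says of the EDSS analyses: "These analyses are done for the double-blind period and the combined double-blind and OLE periods". A further analysis runs from first satralizumab dose. It has no comparator, so its only output is Kaplan-Meier curves and event-free rates.

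**The concern.** A reader of a long-term disability curve will take an event to mean that function was lost. As written, one score over the threshold is enough, and the patient stays an event even if the next score is back at baseline. Section 1.1.1 says that disability in NMOSD mostly follows from relapses and that secondary progression is uncommon. The informative question is therefore how much relapse-related loss remains, and an unconfirmed event cannot answer it.

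The problem also grows with follow-up. Each further visit is another chance for a stable patient to cross the threshold, so the event-free rate drifts down with time. In the randomized comparison both arms share this. In the analysis from first dose no control arm would reveal it.

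**Working it through.** **Is there a confirmation rule?** Section 6.5 gives the event, the model and the outputs, with no confirmation. Section 4.5.6.2 has only the 24-hour symptom rule. No other section requires a sustained rise. The plan states no error rate, event count or power for this endpoint, so there is no figure to reproduce. Everything below is illustrative.

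**Visits.** Three years at 24-week intervals: 3 × 365.25 / (7 × 24) = 6.5, taken as 6. A total of 12 visits for parent plus rollover follow-up is an assumption (12 × 24 = 288 weeks, about 5.5 years), because the documents do not state parent-study durations.

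**Chance of at least one false event in a stable patient.** With an assumed per-visit rate q, independent between visits, this is 1 − (1 − q)^k:

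| q (assumed) | k = 6 | k = 12 |
|---|---|---|
| 1% | 5.9% | 11.4% |
| 2% | 11.4% | 21.5% |
| 3% | 16.7% | 30.6% |
| 5% | 26.5% | 46.0% |

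**Simulation with a shared reference score.** 100,000 patients per scenario; true EDSS 2.0 to 6.0; scores rounded to half points; assumed measurement SD 0.25, 0.35 or 0.5; threshold 1.0 point (2.0 from an observed zero). Percentage of stable patients with a false event:

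| Definition | Visits | SD 0.25 | SD 0.35 | SD 0.5 |
|---|---|---|---|---|
| Unconfirmed, baseline reference | 6 | 10.8 | 24.3 | 42.1 |
| Unconfirmed, baseline reference | 12 | 15.0 | 32.1 | 53.9 |
| Unconfirmed, previous-visit reference | 6 | 15.7 | 38.7 | 68.0 |
| Unconfirmed, previous-visit reference | 12 | 28.6 | 63.1 | 90.0 |
| Confirmed at next visit, baseline reference | 6 | 1.9 | 6.4 | 15.2 |
| 2-point rise, unconfirmed, baseline reference | 6 | 0.0 | 0.2 | 3.6 |
| 2-point rise, unconfirmed, baseline reference | 12 | 0.0 | 0.3 | 5.8 |

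Three things follow.

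- With a fixed baseline, false events accumulate more slowly than the independence formula implies. At SD 0.25 the simulated per-visit rate is 2.7%, for which the formula gives 1 − 0.973^6 = 15.1% over 6 visits, against 10.8% simulated.
- Confirmation removes most false events but not all, because a baseline score that was too low by error stays in every later comparison. The confirmed row also omits a rise first seen at the sixth visit, which cannot be confirmed.
- The 2-point endpoint is little affected by rater noise.

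**Share of counted events that are false.** If true sustained worsening is 3% per year (assumption), over 6 visits with a baseline reference the share is 58%, 77% and 88% for the three SDs without confirmation, and 23%, 53% and 75% with it.

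**Effect on the hazard ratio.** With equal noise n in both arms, observed HR = (HR × h + n) / (h + n). For an assumed true HR of 0.50 and placebo hazard h = 0.10 per year:

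- n = 0.02: 0.07 / 0.12 = 0.58
- n = 0.05: 0.10 / 0.15 = 0.67
- n = 0.10: 0.15 / 0.20 = 0.75

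**The case against.** The definition is a deliberate choice. Section 6.5 keeps endpoint definitions in line with the parent studies so that the data can be summarised together, and the stated objective is time to worsening, not sustained progression. This stands, and it is a good reason not to displace the existing analysis. It is no reason against adding a second one.

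Section 6 defers detailed methods to a separate SAP, which is not among the documents. A confirmation rule could be there, so the finding is that the plan as supplied has none.

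The wording of the event is open. If the whole relapse definition is imported, including symptoms attributable to NMOSD and no confounding cause, pure rater noise is partly screened out and the stable-patient figures overstate it. The endpoint would then largely repeat time to relapse, and recovered relapses would still count. If only the score threshold is meant, noise counts in full. A reader might also infer that scores taken during an acute relapse trigger the event. The documents do not establish this: Section 6.5 speaks of EDSS at scheduled visits and does not say whether relapse-visit scores enter this endpoint.

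The consequences are bounded. All efficacy endpoints are secondary, the primary objective is safety, mean EDSS change is also reported, and Section 4.5.7 asks for the same assessor where feasible. Confirmation has its own hazard: patients who worsen and then leave would be censored as event-free, which could flatter the curve. The fix has to deal with that.

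**Conclusion.** The point holds as a gap in the analysis of a secondary endpoint. A single rise is enough for both EDSS endpoints, and the event-free rates from first dose cannot be read as freedom from lasting disability. At an assumed 2-3% per visit with independence, 11-17% of stable patients have a false event over about 6 visits and 22-31% over an assumed 12. Shared baseline error would slow that accumulation, and a previous-visit reference would worsen it.

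Four stronger readings are not supported:

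- That most reported worsening will be noise. The simulated shares depend on assumed error and true-worsening rates that the documents do not give.
- That the flaw favours satralizumab. Equal noise moves the hazard ratio towards 1 and lowers event-free rates.
- That confirmation all but eliminates false events. Formula 1 − (1 − q²)^11 gives 0.4-1.0% for q = 2-3% over 12 visits, but only if fluctuations are independent. With a shared baseline, 1.9-15.2% remain over 6 visits in the simulation.
- That severe worsening has the same noise problem. It does not (0-5.8%); there the issue is mainly recovered versus lasting relapse-related loss.

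**What to change.** Keep the parent-study definition as it stands, for comparability. Add a pre-specified analysis of confirmed worsening:

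- **Event:** an EDSS rise meeting the relapse-definition threshold, measured from randomization or first satralizumab dose, and still present at the next scheduled 24-week EDSS visit. Date the onset to the first rise.
- **Patients who stop:** allow the end-of-treatment or end-of-study EDSS to confirm. The confirmation interval may then be shorter than 24 weeks.
- **Relapse visits:** a relapse-visit score may not serve as the confirming score.
- **Unconfirmable last-visit rises:** report the analysis twice, counting them as events and as censored, so that the effect of patients who worsen and leave is visible.
- **Severe worsening:** applying the same rule is optional, mainly to separate recovered from lasting loss.

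For the retained analysis, state whether the full relapse definition or only its score threshold applies, which score is the reference, and whether relapse-visit or unscheduled scores count.

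The cost is SAP wording and one more table and curve; the visits are already scheduled. The downsides are fewer events, some late rises left unresolved, and residual false events from baseline-score error.

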6.5.1 Further Analyses

6.5.1.1 Subgroup Analysis

The subgroup summary tables for TFR based on iPDRs will be presented by AQP4-IgG serostatus at screening (positive/negative), age (adolescents/adults) at randomization, geographical region (Asia, Europe, North America), weight at randomization, first dose of satralizumab, ARR at randomization (less than one/one/more than one), most recent attack at randomization (first attack vs relapse), prior therapy at randomization (B-cell depleting therapy/immunosuppressants/others), EDSS at randomization/first dose of satralizumab (<2.5: no or minimal disability/>2.5), race, and Study Identifier of parental study. ARR was a stratification factor in Study BN40898 and is calculated on the basis of the relapses entered in the medical history for Study BN40900. Most recent attack and prior therapy were stratification factors in Study BN40900 and are only available for patients enrolled from this trial.

Further details will be described in the SAP.

6.6 SAFETY ANALYSES

All safety analyses will be performed on the SAF. Safety variables to be assessed are AEs, AESIs, SAEs, selected AEs, injection site reactions, patient withdrawals due to AEs, change in 12-lead ECGs, measurements of laboratory parameters, and vital signs (including body weight).

Summary tables for number and percentage of patients and rate of AEs per 100PY with adverse drug reactions (i.e., AEs related to study drug as assessed by the investigator) will be generated.

Adverse events will be summarized by System Organ Class (SOC) and Preferred Term (PT), on the basis of Medical Dictionary for Regulatory Activities (MedDRA) coding, and grade of severity. The incidence of treatment emergent AEs will also be displayed by severity and relationship to the study drug, respectively. In addition, the incidence of AEs leading to withdrawal from treatment and SAEs will be tabulated.

Incidence of Selected AEs (see Section 5.2.4) will be tabulated. AEs will be further analyzed according to whether they meet Sampson's criteria for diagnosis of anaphylaxis (Sampson et al. 2006).

Laboratory values (including hematology, blood chemistry, and urinalysis), frequencies of laboratory abnormalities, vital signs (temperature, blood pressure, and pulse rate), 12-lead ECG, and suicidality (C-SSRS) will be summarized. Measurement and change from baseline in continuous laboratory parameters (hematology, clinical chemistry, and

urinalysis), continuous ECG, vital signs (blood pressures and pulse rate), and body weight will be summarized with use of descriptive statistics. Body weight by change from randomization/first dose of satralizumab of more than/less than 7% and 15% will also be analyzed descriptively. When analyzing categorical data, the number and percentage of patients in each category will be presented. In addition, shift tables may be used to evaluate the number and percentage of patients having a different post-baseline status when compared with their baseline status. Numbers of patients who meet the marked abnormality criterion will also be presented.

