1.2 BACKGROUND ON SATRALIZUMAB

Satralizumab (RO5333787; ENSPRYNG®) is a humanized anti-human IL-6R blocking monoclonal antibody that was designed by application of recycling antibody technology.

Antibody engineering techniques were utilized to give satralizumab pH-dependent binding affinity to IL-6R so that it binds to IL-6R under neutral conditions in plasma but dissociates under the slightly acidic conditions in endosomes, and is recycled to the plasma instead of being degraded in lysosomes, resulting in a longer plasma half-life. In addition, satralizumab is a modified IgG2 isotype, which reduces Fc-mediated effector functions.

The Clinical Development Program of satralizumab in NMOSD currently consists of two ongoing pivotal placebo-controlled, randomized, double-blind Phase III studies: Study BN40898 in adult and adolescent patients treated with 120 mg subcutaneous (SC) satralizumab in addition to background immunosuppressive therapy (IST) and Study BN40900 in adult patients treated with 120 mg SC satralizumab as a monotherapy. Both studies are ongoing in their open-label extension (OLE) periods.

Data from the completed double-blind periods of the pivotal Phase III Studies BN40898 (Yamamura et al. 2019) and BN40900 (Traboulsee et al. 2020) in adult and adolescents with NMOSD demonstrated a substantial magnitude of clinical benefit. Treatment with satralizumab led to significant reductions in the risk of protocol-defined relapse of 62% in

Study BN40898 (hazard ratio [HR]=0.38; 95% CI: 0.16 to 0.88) and 55% in Study BN40900 (HR=0.45; 95% CI: 0.23 to 0.89) compared with placebo.

Benefit was evident across multiple subgroups and was particularly high in the subgroup of patients who were AQP4-IgG seropositive, with risk reductions of 79% (HR=0.21; 95% CI: 0.058 to 0.750; p=0.0086) and 74% (HR=0.26; 95% CI: 0.108 to 0.627; p=0.0014) in Studies BN40898 and BN40900, respectively. Evidence of benefit in the subgroup of patients who were AQP4-IgG seronegative was inconclusive.

Based on the results of the studies summarized above, satralizumab (ENSPRYNG) has been approved by multiple Health Authorities as monotherapy or in combination with IST for the treatment of NMOSD in adult and adolescent patients who are anti-AQP4 seropositive, and is currently under review by other Health Authorities worldwide.

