4.4.1 Permitted Therapy

Patients are permitted to use the following therapies during the study:

- Background IST with any of the drugs listed below is permitted. The dose must not exceed the dose defined below. Initiation, change or termination of background IST is permitted.

- AZA^a: 3 mg/kg/day
- MMF^a: 3000 mg/day
- Oral corticosteroids: 15 mg/day (prednisolone equivalent)

^a Combination with oral corticosteroids (15 mg/day [prednisolone equivalent]) can be continued in patients who were aged 12 to 17 years at the time of informed consent in Study BN40898.

- Acute relapse (rescue) therapy for NMOSD relapse; pulse intravenous or oral corticosteroids, intravenous IG, and/or apheresis (including plasma exchange and plasmapheresis).

Acute relapse therapy should be provided at the discretion of the Investigator after the EDSS/Functional System Score (FSS) assessment has been completed at a relapse assessment visit (except when urgent treatment is required before the patient can undergo this assessment). Satralizumab treatment can be continued as scheduled, concurrently with acute relapse therapy.

- Treatment with corticosteroids (e.g., oral, nasal) for AEs (i.e., indications other than background IST or acute relapse therapy) is permitted; the treatment duration should be kept as short as possible.

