4.5.4 Physical Examinations

Limited, symptom-directed physical examinations should be performed at baseline and specified post-baseline visits and as clinically indicated. Changes from baseline abnormalities should be recorded in patient notes. New or worsened clinically significant abnormalities should be recorded as adverse events on the Adverse Event eCRF. In addition, height will be obtained at baseline and weight will be obtained at the specified visits.

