5.3.5.6 Abnormal Vital Sign Values

Not every vital sign abnormality qualifies as an adverse event. A vital sign result must be reported as an adverse event if it meets any of the following criteria:

- Is accompanied by clinical symptoms
- Results in a change in study treatment (e.g., dosage modification, treatment interruption, or treatment discontinuation)
- Results in a medical intervention or a change in concomitant therapy
- Is clinically significant in the investigator's judgment

It is the investigator's responsibility to review all vital sign findings. Medical and scientific judgment should be exercised in deciding whether an isolated vital sign abnormality should be classified as an adverse event.

If a clinically significant vital sign abnormality is a sign of a disease or syndrome (e.g., high blood pressure), only the diagnosis (i.e., hypertension) should be recorded on the Adverse Event eCRF.

Observations of the same clinically significant vital sign abnormality from visit to visit should only be recorded once on the Adverse Event eCRF (see Section [5.3.5.4](#) or details on recording persistent adverse events).

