6.1.3 Safety Analysis Populations

All safety variables will be analyzed on the basis of the Safety Population (SAF). The SAF population will include all randomized or enrolled patients who have received at least one dose of study drug either during the parental studies or this study. It will encompass all patients from the parent studies, even if they do not participate in this study. Patients will be analyzed as treated for analysis purposes in the SAF.

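### The fixed 7% and 15% weight-change categories in Section 6.6 cover adolescents as well as adults, so normal growth can be counted as weight gain in that table

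*Combined protocol and SAP*

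**What the plan says.** Section 6.6 places every safety analysis on the SAF and gives this rule for weight: "Body weight by change from randomization/first dose of satralizumab of more than/less than 7% and 15% will also be analyzed descriptively". No age handling is stated for the weight summaries.

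Section 6.1.3 defines the SAF as the dosed patients of the parent studies and this study, and adds: "It will encompass all patients from the parent studies, even if they do not participate in this study". It sets no age limit.

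Section 1.2 describes "Study BN40898 in adult and adolescent patients". Section 4.4.1 gives the age range, in saying that combining azathioprine or mycophenolate with oral corticosteroids "can be continued in patients who were aged 12 to 17 years at the time of informed consent in Study BN40898".

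Section 6.5.1.1 lists "age (adolescents/adults) at randomization" among the subgroups for time to first relapse. No such split is stated for weight.

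**The concern.** A fixed percentage cut means different things in a grown and a growing patient. In an adult, a gain of 15% deserves a look. In an adolescent followed for several years it may be ordinary growth.

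The change is counted from parent-study randomization or first satralizumab dose, so growth during the parent study stays in the figure even if the patient has turned 18 before rolling over. This study adds up to 3 years (Sections 1.3 and 3.1.1).

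The gain rows would then mix growth with any drug-related gain. In the other direction, growth can offset a true loss, and a patient who stops growing can sit in the no-change group. The adolescents could not be picked out of the pooled table. What is at stake is how readable one descriptive table is, in a study whose primary objective is long-term safety.

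**Working it through.** The plan gives no figure to reproduce. The first step is to follow the text:

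1. Population of the weight table: the SAF (Section 6.6).
2. SAF: dosed patients of both parent studies, with no age limit (Section 6.1.3).
3. BN40898: included adolescents (Section 1.2), aged 12 to 17 at consent (Section 4.4.1).
4. Start of the change: randomization or first dose (Section 6.6), both possible while the patient is under 18.
5. Cuts: 7% and 15% for everyone (Section 6.6).

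Growth can therefore be counted as gain. How fast depends on weights and growth rates that the documents do not give. **All weights and rates below are assumptions**, with growth held constant in kg per year.

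*Time for growth alone to reach a cut* = cut × starting weight ÷ annual gain.

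| Assumed case | +7% | +15% |
|---|---|---|
| Fast: 40 kg, 5 kg/year | 0.07 × 40 ÷ 5 = 0.56 years | 0.15 × 40 ÷ 5 = 1.2 years |
| Middle: 45 kg, 3 kg/year | 0.07 × 45 ÷ 3 = 1.05 years | 0.15 × 45 ÷ 3 = 2.25 years |
| Near-adult: 55 kg, 0.5 kg/year | 0.07 × 55 ÷ 0.5 = 7.7 years | 0.15 × 55 ÷ 0.5 = 16.5 years |

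The first two cases cross both cuts within 3 years; the near-adult case crosses neither.

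*Shortfall shown as no change*, flat weight for 3 years:
- Middle case: expected 45 + 3 × 3 = 54 kg. The table shows 0%, but the patient is 1 − 45/54 = 16.7% below expectation.
- Near-adult case: expected 55 + 3 × 0.5 = 56.5 kg. The gap is 1 − 55/56.5 = 2.7%.

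*Effect on the pooled +15% row.* Let N be the SAF size, k the number of adolescents who all cross, and p the share of adults who cross. Pooled minus adult-only share = [(N − k)p + k]/N − p = (k/N)(1 − p), or (1 − p)/N per adolescent.
- N = 150, p = 10%: 0.9 ÷ 150 = 0.60 percentage points.
- N = 250, p = 30%: 0.7 ÷ 250 = 0.28 percentage points.

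N is assumed above 127 because the figure of about 127 in Section 6.2 is the expected maximum number enrolled here, and the SAF also counts parent-study patients who do not roll over.

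**The case against.** **This is detail for a later SAP.** Section 6 defers detailed methods to a SAP whose text is not in the supplied documents, and an age split of one table could be placed there. A reader might infer that no split will ever be made; the documents do not support that. But Section 6.6 does state a rule, with its cuts, starting point and population, and the deferral does not alter the rule as written.

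**Nothing depends on the table.** It is descriptive, the dose is a fixed 120 mg, and weight change is not among the satralizumab or class risks set out in Section 5.1. This stands and keeps the point small.

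**A safety signal could be hidden.** A reader might infer this, but the masking is confined to this table. Section 4.5.4 says: "New or worsened clinically significant abnormalities should be recorded as adverse events on the Adverse Event eCRF". Section 5.3.5.6 says: "A vital sign result must be reported as an adverse event if it meets any of the following criteria", and the criteria include clinical significance; Section 6.6 counts body weight among the vital signs.

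**There is a placebo reference.** The parent studies are "two ongoing pivotal placebo-controlled, randomized, double-blind Phase III studies", so a from-randomization table could have a comparator in the double-blind period. It would have none in the later years, which are what this study adds.

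**Height.** A reader might infer that growth in stature and excess weight can never be separated, because height is taken at baseline only. Section 4.5.4 and Appendix 1 say that of WN42349 alone. The table starts in the parent studies, whose height schedules are not in the documents, so the inference is not supported.

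**Conclusion.** The point holds as a cheap improvement. Applied as written, the fixed categories can count normal growth as gain and can show a growth shortfall as no change.

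The size is unknown and probably small. The growth times and the 0.28 to 0.60 points per adolescent are illustrations that rest on assumed weights, growth rates, SAF sizes and adult crossing shares; they do not show that any particular patient will be misclassified. A reader might be tempted to divide a guessed number of adolescents by 127 and report a shift of several points. The documents do not support that, because they give no adolescent count and 127 is not the SAF. No main conclusion of the study is affected.

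**What to change.** In Section 6.6 or the SAP, present the 7% and 15% categories for patients aged 18 or over at the baseline used for the change, whether randomization or first dose. Show patients under 18 at that time separately, as a listing or individual weight profiles with age and sex. Weight-for-age-and-sex z-scores are optional, and only within the age range of a growth reference named in the SAP.

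The cost is one sentence and one split display. The weights are those that the planned table already uses, and Section 6.4 already plans age and sex summaries at parent-study baseline and at first dose for all originally randomized or enrolled patients, so no new data are needed.

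The downside is one small, imprecise extra display. It would not isolate a satralizumab effect, not least because these patients may also be taking oral corticosteroids (Section 4.4.1).
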